9.2.5. Pharmacokinetics Analyses

PK concentration will be summarized. Additional PK and PK/PD analyses will be conducted as deemed appropriate and may be reported separately from the Clinical Study Report.

9.2.6. Pharmacodynamics Analyses

The exploratory PD endpoints (changes over time in $\alpha_4\beta_7$ and $\alpha_4\beta_1$ receptor occupancies and blood CCR9 mRNA level) will be summarized descriptively. Additional analysis of PD endpoints may be described in a biomarker analysis plan separate from the study SAP and reported separately. The PD Population will be used for the summarization and analysis of PD exploratory endpoints.

9.3. Analyses for Induction Period, 52-week Treatment Period, and LTE Period

The Treatment Period in the main part of the study includes the 12-week Induction Period and the 40-week Maintenance Period. For the purpose of statistical analyses, the Induction Period and the Maintenance Period will be treated as 2 independent parts. There will be 2 analyses planned: one for the 12-week Induction Period (i.e., the period for the primary efficacy endpoint) and one for the 52-week Treatment Period (i.e., the 12-week Induction Period plus the 40-week Maintenance Period and Safety Follow-up Period). The details of the analyses will be described in the SAP. Additional analysis of the optional 52-week LTE Period for the participants enrolled into the LTE Period will also be performed as appropriate.

Induction Period Analysis

The analysis of the 12-week Induction Period will be performed after all the participants have completed the Week 12 assessments or discontinued the study before the Week 12 assessments. The analysis will formally evaluate the primary and secondary efficacy endpoints, all the exploratory efficacy endpoints defined by Week 12, and safety of MORF-057 vs placebo during

the 12-week Induction Period. The PK and PD data during the 12-week Induction Period will also be summarized.

52-week Treatment Period Analysis

The analysis of the 52-week Treatment Period will be performed after all the participants have completed the Week 52 assessments (and Safety Follow-up Period for participants not rolling over into the LTE Period) or discontinued from the study during the 52-week Treatment Period. The analysis will formally evaluate the efficacy (including all the exploratory efficacy endpoints defined by Week 52), PK, PD, and safety of MORF-057 during the 52-week Treatment Period (and the Safety Follow-up Period for participants not rolling over into the LTE Period). The cumulative data, including those from the Induction Period, will be used in this analysis.

52-week LTE Period Analysis

The analysis of the LTE Period will be performed after all the participants enrolled into the LTE Period have completed the 52-week LTE Period and the Safety Follow-up Period or discontinued the study during the LTE Period. The analysis will evaluate the long-term safety of MORF-057 and selected efficacy endpoints at Week 104 as appropriate during the LTE Period plus the Safety Follow-up Period.

9.4. Interim Analysis

The analysis of the 12-week Induction Period (Induction Period Analysis) will be performed after all the participants have completed the Week 12 assessments or discontinued the study before the Week 12 assessment, as described in Section 9.3.

An independent DSMB will review participant safety data and monitor scientific integrity throughout the study. Details related to the DSMB will be clearly delineated in the DSMB Charter.

9.5. Sample Size Determination

The sample size was determined based on the primary endpoint of clinical remission at Week 12 by using the Chi-Squared Test to compare two proportions. A sample size of 70 participants per group (giving a total of 280) will provide 80% power to detect a difference of 15% in the clinical remission rate between MORF-057 and placebo, based on the use of a two-sided test at the alpha=0.10 level of significance. The calculation is based upon an assumed placebo remission rate of 7%.

10. Appendices: Supporting Documentation and Operational Considerations

10.1. Appendix 1: Regulatory, Ethical, and Study Oversight Considerations

10.1.1. Regulatory and Ethical Considerations

This study will be conducted in accordance with the protocol and with the following:

- Consensus ethical principles derived from international guidelines including the Declaration of Helsinki and Council for International Organizations of Medical Sciences (CIOMS) international ethical guidelines
- Applicable International Council for Harmonisation (ICH) Good Clinical Practice (GCP) guidelines
- Applicable laws and regulations, including European Union Clinical Trials Regulation 536/2014

The protocol, protocol amendments, ICF, IB, and other relevant documents (e.g., advertisements) must be submitted to an IRB/IEC or to the Member States Concerned and reviewed and approved by the IRB/IEC or Member States Concerned, as applicable, before the study is initiated.

Any amendments to the protocol will require IRB/IEC or Member States Concerned, as applicable, approval before implementation of changes made to the study design, except for changes necessary to eliminate an immediate hazard to study participants.

Protocols and any substantial amendments to the protocol will require Member States Concerned or health authority, as applicable, approval prior to initiation, in line with country-specific requirements.

The Investigator will be responsible for the following:

- Providing written summaries of the status of the study to the IRB/IEC annually or more frequently in accordance with the requirements, policies, and procedures established by the IRB/IEC, as applicable
- Notifying the IRB/IEC of SAEs or other significant safety findings as required by IRB/IEC procedures, as applicable
- Providing oversight of the conduct of the study at the site and adherence to requirements of 21 CFR, ICH guidelines, the IRB/IEC or Member States Concerned, as applicable, European Union Clinical Trials Regulation 536/2014 for clinical studies, and all other applicable local regulations

After reading the protocol, each Investigator will sign the Investigator's Agreement page (Section 10.10). The study will not start at any study center at which the Investigator has not signed the protocol.

The Sponsor will notify the authorities as applicable (in line with country/region requirements) about a serious breach of the regulations or of the version of the protocol applicable at the time of the breach. A 'serious breach' means a breach likely to affect to a significant degree the safety and rights of a participant or the reliability and robustness of the data generated in the clinical trial.

If the Investigator identifies a potential instance of a serious breach, the Sponsor and Contract Research Organization (CRO) should be notified immediately at **CCI** [REDACTED]
Include any available information at the time of the incident and copies of all documentation, if any, supporting the suspicion.

10.1.2. Financial Disclosure

Investigators and sub-Investigators will provide the Sponsor with sufficient, accurate financial information as requested to allow the Sponsor to submit complete and accurate financial certification or disclosure statements to the appropriate regulatory authorities. Investigators are responsible for providing information on financial interests during the course of the study and for 1 year after completion of the study.

10.1.3. Insurance

The Sponsor has obtained liability insurance, which covers this study as required by local law and/or national regulations and/or ICH guidelines, whichever is applicable. The terms of the insurance will be kept in the study files.

10.1.4. Informed Consent Process

The Investigator or his/her representative will explain the nature of the study, including the risks and benefits, to each participant or his/her legally acceptable representative, if applicable, and answer all questions regarding the study.

Participants must be informed that their participation is voluntary. Each participant or his/her legally acceptable representative, if applicable, will be required to sign a statement of informed consent that meets the requirements of 21 CFR 50, local regulations, ICH guidelines, privacy and data protection requirements, where applicable, Member States Concerned/the IRB/IEC or study center.

The medical record must include a statement that written informed consent was obtained before the participant was enrolled in the study and the date the written consent was obtained. The authorized person obtaining the informed consent must also sign the ICF.

If a participant or legal representative is unable to read and/or write, an impartial witness should be present during the entire informed consent discussion.

Participants must be re-consented to the most current version of the ICF(s) during their participation in the study.

A copy of the ICF(s) must be provided to the participant or his/her legally acceptable representative, if applicable.

Additional Consents

The main ICF will contain separate sections for the following additional consents:

- Optional collection of blood, colonic tissue, and stool samples for future PD, microbiome-related analyses, fecal calprotectin assessment, and future research. If consent is provided, use of the remaining blood and colonic tissue samples from the study-required procedures may also be used for future research, including future PK research (see Sections 8.7.1, 8.10, 8.12, and the SoA in Section 1.2).

- Optional blood sampling for future pharmacogenomics analysis, which will involve genetic testing (see Section 8.12, Section 10.9, and the SoA in Section 1.2).

Additional ICFs will be provided to participants or their partners for review and signature, as needed:

- Optional LTE Period (see Section 4.1 and the SoA in Section 1.2)
- Consent to courier deliveries/pick-ups (see Section 8.13)
- Pregnancy Follow-up (see Section 8.9.5)

The Investigator or authorized designee will explain to each participant the objectives of the optional sampling. Participants will be told that they are free to refuse to participate and may withdraw their consent at any time and for any reason during the sample storage period (determined based on local country regulations). Signatures will be required to document a participant's agreement to allow the optional samplings. Participants who decline to participate in optional samplings will not be asked to provide signatures.

10.1.5. Data Protection

- Measures must be described that will be implemented to ensure confidentiality of records containing personal data of participants. In particular, the personnel of the site, Sponsor, and vendors (CRO) involved in data processing are bound by obligations of confidentiality and the participants will be assigned a unique identifier by the Sponsor. Any participant records or datasets that are transferred to the Sponsor will contain the identifier only; participant names or any information which would make the participant identifiable will not be transferred.

The participant must be informed that his/her personal study-related data will be used by the Sponsor in accordance with local data protection law. The level of disclosure must also be explained to the participant. In particular, the participant must be informed that his/her medical records may be examined by Clinical Quality Assurance auditors or other authorized personnel appointed by the Sponsor, by appropriate IRB/IEC members or Member States Concerned members, as applicable, and by inspectors from regulatory authorities.

- The contract between Sponsor and study sites specifies the responsibilities of the parties regarding data protection, including handling of data security breaches and respective communication and cooperation of the parties. The process to handle data security breaches, in order to mitigate the possible adverse effects of such breaches to the privacy of study participants, must be described.
- Organizational and technical arrangements that will be implemented to avoid unauthorized access, disclosure, dissemination, alteration, or loss of personal data must be described. In particular, the information technology systems used to collect, process, and store study-related data are secured by technical and organizational security measures designed to protect such data against accidental or unlawful loss, alteration, or unauthorized disclosure or access.

10.1.6. Data and Safety Monitoring Board

A DSMB has been appointed to this study. The DSMB is a group of independent clinicians/scientists who are appointed to monitor the safety and scientific integrity of a human research treatment, and to make recommendations to the Sponsor regarding the modification, continuance, or stopping of a study based on assessments of safety. The composition, responsibilities, and meeting schedules of the DSMB will be described in a separate charter.

10.1.7. PML Adjudication Committee

A PML Adjudication Committee will oversee a PML RAMP to monitor all participants for PML. The composition, responsibilities, and meeting schedules of the PML Adjudication Committee will be described in a separate charter.

10.1.8. Dissemination of Clinical Study Data

The Sponsor will submit a summary of the results of the clinical study to the relevant clinical study databases (including clinicaltrials.gov and the public domain of the Clinical Trials Information System database at <https://euclinicaltrials.eu/home>) in a timely manner. As appropriate, this will be accompanied by a summary written in a manner that is understandable to laypersons.

10.1.9. Data Quality Assurance

All participant data relating to the study will be recorded on paper-based Case Report Forms (CRFs) or eCRFs unless transmitted to the Sponsor or designee electronically (e.g., laboratory data). The Investigator is responsible for having quality system processes and procedures in place verifying that CRF data entries against source data are accurate and correct. The Investigator is responsible for ensuring source records are maintained in real-time, eCRFs are completed per eCRF Completion Guidelines, and physically or electronically signing the CRF.

Guidance on completion of CRFs and eCRFs will be provided in the corresponding guidelines.

The Investigator must permit study-related monitoring, audits, IRB/IEC review (if applicable), and regulatory agency inspections and provide direct access to source data documents.

Monitoring details describing strategy, including definition of study critical data items and processes (e.g., risk-based initiatives in operations and quality such as risk management and mitigation strategies and analytical risk-based monitoring), methods, responsibilities, and requirements, including handling of non-compliance issues and monitoring techniques (central, remote, or on-site monitoring) are provided in the Monitoring Plan.

The Sponsor or designee is responsible for the data management of this study, including scheduled data audits and verification against original source data/documentation.

The Sponsor assumes accountability for actions delegated to other individuals (e.g., CROs).

The contents of the electronic Trial Master File pertaining to the conduct of this study must be retained by the Sponsor and the Investigator for at least 25 years after study completion unless local regulations, institutional policies, or by an agreement with the Sponsor require a longer retention period. However, the medical files of participants shall be archived in accordance with national law. It is the responsibility of the Sponsor to inform the Investigator/institution as to when these documents no longer need to be retained.

Please reference the current version of ICH E6 for the minimum list of essential documents required for the conduct of a clinical trial. Additional documentation may be required by the Sponsor or CRO before, during, and after completion of the trial.

No records may be destroyed during the retention period without the written approval of the Sponsor. No records may be transferred to another location or party without written notification to the Sponsor.

10.1.10. Source Documents

Source documents provide evidence for the existence of the participant and substantiate the integrity of the data collected. Source documents are filed at the Investigator's site and digitized copies are maintained in the site section of the electronic Trial Master File.

Data reported on the CRF or entered in the eCRF that are transcribed from source documents must be consistent with the source documents or the discrepancies must be explained by the Investigator and documented in the CRF. The Investigator may need to request previous and current medical records or transfer records as source documents for participants involvement (or enrollment) in this study.

The Investigator must maintain accurate documentation (source data) that supports the information entered in the CRF and eCRF.

Sponsor-designated study monitors will perform ongoing source data verification to confirm that data entered into the CRF/eCRF by authorized site personnel are accurate, complete, and verifiable from source documents; that the safety and rights of participants are being protected; and that the study is being conducted in accordance with the currently approved protocol and any other study agreements, ICH GCP, and all applicable regulatory requirements.

10.1.11. Study and Site Start and Closure

10.1.11.1. First Act of Recruitment

The study start date is the date on which the clinical study will be open for recruitment of participants (i.e., when the first site is open).

10.1.11.2. Study/Site Termination

The Sponsor or designee reserves the right to close the study site or terminate the study at any time for any reason at the sole discretion of the Sponsor. Study sites will be closed upon study completion. A study site is considered closed when all required documents and study supplies have been collected, all quality compliance activities have been completed, and a study site closure visit has been performed.

The Investigator may initiate study site closure at any time, provided there is reasonable cause and sufficient notice is given in advance of the intended termination.

Reasons for the early closure of a study site by the Sponsor or Investigator may include but are not limited to:

- Failure of the Investigator to comply with the protocol, the requirements of the Member States Concerned or IRB/IEC, as applicable, or local health authorities, the Sponsor's procedures, or GCP guidelines
- Inadequate or no recruitment (evaluated after a reasonable amount of time) of participants by the Investigator
- Total number of participants enrolled earlier than expected

Reasons for study termination include, but are not limited to:

- Recommendation of the DSMB based on the ongoing review of safety
- If a positive benefit/risk ratio is no longer observed, based on DSMB review of unblinded data
- Discontinuation of further study drug development

If the study is prematurely terminated or suspended, the Sponsor shall promptly inform the Investigators, the Member States Concerned and/or the IRBs/IECs, as applicable, the regulatory authorities, and any CROs used in the study of the reason for termination or suspension, as specified by the applicable regulatory requirements. The Investigator shall promptly inform the participant and should assure appropriate participant therapy and/or follow-up.

10.1.12. Publication Policy

The results of this study may be published or presented at scientific meetings. If this is foreseen, the Investigator agrees to submit all manuscripts or abstracts to the Sponsor before submission. This allows the Sponsor to protect proprietary information and to provide comments.

The Sponsor will comply with the requirements for publication of study results. In accordance with standard editorial and ethical practice, the Sponsor will generally support publication of multicenter studies only in their entirety and not as individual site data. In this case, a coordinating Investigator will be designated by mutual agreement.

Authorship will be determined by mutual agreement and in line with International Committee of Medical Journal Editors authorship requirements.

10.2. Appendix 2: Progressive Multifocal Leukoencephalopathy Checklists

Subjective PML Checklist

Symptoms	“Compared to how you usually feel, have you had a significant change in any of the following?”		If the answer is “Yes,” obtain a description of the symptom(s) with examples.	Applicable Objective Test(s): Document results on PML Objective Checklist
	Yes	No		
1. Have you been experiencing any persistent difficulty with your vision, such as loss of vision or double vision? Have you been having trouble with reading?				Test visual fields and ocular motility.
2. Have you been experiencing any persistent difficulty speaking or having your speech understood by others?				Casual observation of speech output for dysarthria or aphasia. Ask patient to name a few objects and repeat a multipart phrase.
3. Have you been experiencing any persistent weakness in an arm or a leg?				Test for pronator drift (Barré maneuver) and/or fixation on arm roll. Assess the ability to hop on either foot; foot and finger tapping. Test symmetric muscle strength.
4. Have you noticed yourself regularly bumping into things or having difficulty writing?				Ask for spontaneous writing sample and observe finger to nose, heel to shin, and tandem gait.
5. Have you regularly been experiencing difficulty understanding others?				Ability to follow serial commands (close your eyes, stick out your tongue, and touch your left finger to your left ear).
6. Have you had persistent problems with your memory or thinking?				Recall of 3 objects over 1 minute with distraction; ability to follow commands.
7. Have you been experiencing any persistent numbness or other loss of sensation?				Test sensation side to side with pinprick.

PML, progressive multifocal leukoencephalopathy.

Objective PML Checklist – To be completed for participants with positive subjective finding

Perform the objective test(s) that correspond to the subjective checklist finding

Positive Symptom(s)	Applicable Objective Test(s)	Test Result(s)		If test result is abnormal, briefly describe result
		Normal	Abnormal	
1. Difficulty with vision or reading	Test visual field and ocular motility.			
2. Difficulty with speaking	Casual observation of speech output for dysarthria or aphasia. Ask patient to name a few objects and repeat a multipart phrase.			
3. Weakness in an arm or a leg	Test for pronator drift and/or fixation on arm roll. Assess the ability to hop on either foot; foot and finger tapping. Test muscle strength.			
4. Bumping into things or difficulty writing	Ask for spontaneous written sample and observe finger to nose, heel to shin, and tandem gait.			
5. Difficulty understanding others	Ability to follow serial commands (Close your eyes, stick out your tongue, and touch your left finger to your left ear).			
6. Problems with memory or thinking	Recall of 3 objects over 1 minute with distraction; ability to follow commands.			
7. Problems with numbness	Test sensation side to side with pinprick.			

Source: [Parikh 2018](#)

× If objective test corroborates the reported symptom, refer the participant for a Neurology consult. Otherwise, please follow up with the participant one week after the Objective Checklist was administered to ensure symptoms are not recurring.

× Please notify your Clinical Research Associate and the Sponsor of any positive Objective Checklist findings.

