7.1.2. Dose Interruption and Re-challenge

Situations requiring study drug interruption and the potential for re-challenge are presented in [Table 7](#). Decisions regarding dose interruptions and re-challenges will be made by the Investigator in consultation with the Medical Monitor based on the clinical evaluation of the participant.

Table 7. Study Drug Interruption and Re-challenge Guidelines

Clinical Situation/Event	Study Drug Interruption	Re-Challenge
Possible drug-induced liver damage	Requirements are outlined in Table 12	Requirements are outlined in Table 12
PML screening	Requirements for study drug interruption after positive Subjective PML questionnaire are outlined in Section 8.8.5	Requirements for re-challenge are dependent on PML being definitively ruled out as outlined in algorithm within the PML Reference Guide
Serious Adverse Event	Investigator and Sponsor Medical Monitor may interrupt study drug administration if deemed necessary	Re-challenge decision will be made in each clinical situation in consultation with Investigator and Sponsor Medical Monitor

Abbreviations: PML, progressive multifocal leukoencephalopathy.

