8.8.5. Progressive Multifocal Leukoencephalopathy

The Subjective PML Checklist will be administered to participants during Screening. The Subjective PML Checklist (Section 10.2) will also be completed at study visits according to the schedule in the SoA (Section 1.2). If the results of the questionnaire are suggestive of signs and symptoms of PML, hold any further doses of study drug and notify the Medical Monitor. The participant will undergo Objective PML Checklist testing (Section 10.2), a full neurological exam by a neurologist, and, if indicated, additional testing. Study drug may not be resumed until PML has been definitively ruled out.

A participant with confirmed PML will be excluded from the study or will permanently discontinue study drug and will be withdrawn from the study (see Section 7.1.1).

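### After a positive Subjective PML Checklist and a normal objective test, Appendix 2 directs only a one-week follow-up, whereas Section 8.8.5 requires an exam by a neurologist

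*Protocol*

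**What the plan says.** Section 8.8.5 sets one rule for the Subjective PML Checklist. The trigger is "If the results of the questionnaire are suggestive of signs and symptoms of PML". The site must then "hold any further doses of study drug and notify the Medical Monitor". The work-up follows: "The participant will undergo Objective PML Checklist testing (Section 10.2), a full neurological exam by a neurologist, and, if indicated, additional testing". On restarting treatment: "Study drug may not be resumed until PML has been definitively ruled out".

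Table 7 in Section 7.1.2 points to the same rule and names its trigger: "Requirements for study drug interruption after positive Subjective PML questionnaire are outlined in Section 8.8.5". Footnote v to Table 1 and footnote n to Table 2 of the Schedule of Activities also call for a full neurological exam on the strength of the questionnaire, though neither names a neurologist.

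Appendix 2 (Section 10.2) holds the two checklists. The Objective Checklist is headed "To be completed for participants with positive subjective finding". Its first note reads "If objective test corroborates the reported symptom, refer the participant for a Neurology consult", and continues "Otherwise, please follow up with the participant one week after the Objective Checklist was administered to ensure symptoms are not recurring". Its second note asks sites to tell the Clinical Research Associate and the Sponsor about positive objective findings.

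**The concern.** The two texts give different instructions for one combination of results: a positive subjective checklist with a normal objective test. Section 8.8.5 sends that participant to a neurologist; the Appendix 2 note sends the participant to a one-week check and nothing more.

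Appendix 2 is the form that staff have in front of them when the objective tests are done, so its note may well be the instruction they act on. The objective tests are short bedside checks, limited to those matching the reported symptom. Section 8.8.5 does not let a normal result on them stand in for the neurologist. The second note gives no prompt either, because it covers only positive objective findings. What is at stake is a required safety exam in a participant with new neurological symptoms, for a condition that Section 2.3.2.1 describes as fatal. No endpoint or other statistical quantity is affected.

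**Working it through.** No arithmetic applies; the check is a comparison of current texts.

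1. **Do both texts cover the same participants?** Section 8.8.5 speaks of a questionnaire suggestive of PML, and Appendix 2 of a positive subjective finding. Two links join them. Section 8.8.5 itself sends its participants to the Objective Checklist in Section 10.2, so each of them reaches the Appendix 2 notes. Table 7 also describes the Section 8.8.5 trigger as a positive Subjective PML questionnaire.

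2. **Is the neurologist exam in Section 8.8.5 conditional?** No. The sentence lists three things: the Objective Checklist, the neurologist exam and additional testing. The words on indication qualify only the third.

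3. **Is the referral in Appendix 2 conditional?** Yes. It depends on the objective test corroborating the symptom, and the alternative branch contains no referral.

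4. **Set side by side, after a positive subjective checklist:**

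| Objective result | Section 8.8.5 | First note, Appendix 2 |
|---|---|---|
| Corroborates the symptom | Neurologist exam | Neurology consult |
| Normal | Neurologist exam | Follow-up at one week, no referral |

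The texts agree in the first row and conflict in the second.

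5. **Do they conflict on anything else?** No. Appendix 2 is silent on the drug hold and the Medical Monitor, and silence does not cancel Section 8.8.5. The notice to the Clinical Research Associate and Sponsor is additional to the Medical Monitor notice.

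6. **Which text is out of step?** The Appendix 2 note. Section 8.8.5, both Schedule of Activities footnotes and Table 7 (by its reference to Section 8.8.5) all start from the questionnaire, not from the objective test.

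**The case against.** The best defence is that the intended rule is clear. The body text, the Schedule of Activities and Table 7 point one way, and a single form note points the other. Dosing is held, the Medical Monitor knows of the case, and treatment cannot restart until PML is excluded. A PML Adjudication Committee also oversees a risk programme covering all participants, under a charter that is not shown. This stands as a limit on the harm. It does not remove the conflict, because the note still tells sites to do less than Section 8.8.5 requires.

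A second defence is that a suggestive result leaves room for judgement and may be narrower than a positive one. That matters for how the fix is worded. It does not rescue the note: even on the narrower reading, every participant who triggers Section 8.8.5 and has a normal objective test falls into the one-week branch.

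A third is that the PML Reference Guide may settle the matter. It is not shown, and Table 7 cites it only for re-challenge.

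A reader might also infer three stronger things that the documents do not support:

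- *Appendix 2 allows dosing to continue.* It says nothing about dosing, and the hold in Section 8.8.5 applies.
- *The delay can be read from the visit schedule, as the time to the next planned checklist.* That interval is not a bound. A site following the note would omit the exam again if the next objective test were also normal. In the other direction, the hold and the Medical Monitor notice could bring the exam forward.
- *The conditional referral is a deliberate filter.* Nothing in the protocol says so, and Section 8.8.5 and the Schedule of Activities footnotes contain no such filter.

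**Conclusion.** The contradiction is real and should be corrected. For a participant whose Subjective PML Checklist triggers Section 8.8.5 and whose objective test is normal, the protocol both requires a neurologist exam and, in the first Appendix 2 note, directs only a one-week follow-up. It is an inconsistency in a safety procedure, not a question of design.

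The consequence is limited to a neurologist exam that could be skipped or delayed at a site acting on the form. The frequency of this combination of results is not given, the length of any delay cannot be bounded from the documents, and Section 2.2.2 reports no PML case in completed or ongoing studies. The conclusion assumes that the trigger in Section 8.8.5 is what Table 7 calls a positive questionnaire. Whether sites in fact act on the form alone cannot be known from the protocol.

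**What to change.** Replace the first note under the Objective Checklist in Appendix 2 with:

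> For a positive subjective finding, follow Section 8.8.5: hold study drug, notify the Medical Monitor, complete the Objective Checklist, and refer to a neurologist for a full neurological exam whatever the objective result. If the objective test is normal, also follow up one week later; a normal Objective Checklist does not replace the neurologist exam or release the hold.

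Deferring to Section 8.8.5 ties the note to that section's trigger, so it does not create a second rule. Keep the second note, and leave Section 8.8.5, Table 7 and the Schedule of Activities footnotes unchanged. Add no separate clause for people not yet dosed. Section 8.8.5 and footnote v do not distinguish them, so a conditional referral there would reintroduce the conflict; Exclusion Criterion 6 already deals with their eligibility.

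The cost is one reworded note. Under Section 10.1.1 an amendment needs ethics committee or Member State approval, so the change can go into the next amendment, with a memo to sites meanwhile pointing them to Section 8.8.5. It adds no procedure beyond what Section 8.8.5 already requires, provided its trigger is read as Table 7 reads it.
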